### **3 ASSESSMENT AND MANAGEMENT OF RISK**

The additional diagnostic or monitoring procedures do not pose more than minimal additional risk or burden to the safety of the subjects compared to normal clinical practice.

Therefore, this trial is categorised as a low intervention clinical trial.

The risk of adverse events occurring as a consequence of the intervention in this trial is unlikely, therefore safety reporting will be limited to the safety reporting that is necessary in routine care.

## 4 OBJECTIVES AND ENDPOINTS / OUTCOME MEASURES

### 4.1 Primary objective

The primary research question of the trial is to assess whether foot drop, caused by peroneal nerve entrapment in adult patients\* recovers better within 9 months after decompressive surgery compared to prolonged standard conservative treatment.

\* Exclusion of iatrogenic or traumatic peroneal nerve palsies. Exclusion of peroneal nerve compression caused by cysts or tumours. Exclusion of patients with polyneuropathy. Exclusion of other surgical techniques than neurolysis.

Intervention A: Decompressive release of the peroneal nerve at the level of the fibular head in patients with foot drop due to peroneal nerve entrapment.

Intervention B: Prolonged conservative treatment of foot drop due to peroneal nerve entrapment.

Null hypothesis: There is no difference in recovery of foot drop due to peroneal nerve entrapment after intervention A or intervention B.

Alternative hypothesis: Recovery of foot drop due to peroneal nerve entrapment is superior after intervention A compared to intervention B.

### 4.2 Secondary objectives

The secondary objectives of the foot drop trial are:

- To collect pathology-related data in peroneal nerve entrapment.
- To evaluate and compare quality of life data of patients with foot drop due to peroneal nerve entrapment and to assess the evolution of quality of life during conservative/surgical treatment
- To assess and compare follow-up electrophysiological data in patients with peroneal nerve entrapment
- To assess the evolution of gait impairment in patients with foot drop due to peroneal nerve entrapment through a broad range of questionnaires/gait assessments.
- To assess long-term follow-up (18 months after randomization) data after cross-over is allowed (to collect prospective data on long term follow-up).
- To evaluate the cost-effectiveness of both treatment strategies.

### 4.3 Endpoints

#### 4.3.1 Primary endpoint

**The primary endpoint is the difference in distance covered in meters during the six-minute walk test (6MWD) between baseline and 9 months after randomization.** Based on a literature analysis and patient feedback on the trial design, gait analysis and recovery of a normal gait pattern are crucial in the recovery of foot drop. In 88% of interviewed patients, success of treatment was related to gait improvement. The distance covered during the six-minute walk test (6MWD) is validated and clinically used in gait analysis.

#### 4.3.2 Secondary endpoints

##### Key secondary endpoint: time to recovery.

Very limited data is available regarding time to recovery after surgical or conservative treatment in peroneal nerve entrapment (35, 55). Time to recovery is defined as: the time necessary to cover the minimal age- and sex-specific normal 6MWD AND the time necessary for foot drop recovery to an MRC-score  $\geq 4$  for ankle dorsiflexion. The minimal age- and sex-specific normal 6MWD is defined as 82% of the applied reference equations for prediction of the 6MWD (59, 60). The reference value that will be used is  $6\text{MWD}_{\text{pred}}(\text{m}) = 868.8 - (\text{age}_{\text{years}} \times 2.99) - (\text{gender} \times 74.7)$ . The value for gender is 0 in male subjects and 1 in female subjects (60). The reference values and equation are added to the study protocol in Appendix 5.

##### Other Secondary outcomes

1. **Ankle dorsiflexion strength:** measured by the MRC-score and isometric dynamometry at 10 days, 6 weeks, 3 months, 6 months, 9 months and 18 months after randomization. Ankle dorsiflexion strength will also be assessed after 10 days in the surgical arm of the trial.
2. **Gait assessment** at 6 weeks, 3 months, 6 months, 9 months and 18 months after randomization with
  - a. Functional ambulation categories, Stanmore questionnaire
  - b. Gait speed during the 10-meter walk test
  - c. The proportion of patients in both groups who reach minimal normal age- and sex-specific reference values for 6MWD, 9 months after randomization.
  - d. Difference in distance covered in meters during the six-minute walk test between baseline and 6 weeks, 3 months, 6 months and 18 months after randomization
3. **Complications and neurological deficits :**
  - a. Motor changes including MRC-score for ankle eversion and hallux extension at 6 weeks, 3 months, 6 months, 9 months and 18 months after randomization. Motor function will also be assessed after 10 days in the surgical arm of the trial.
  - b. Sensory changes at 6 weeks, 3 months, 6 months, 9 months and 18 months after randomization. Sensory changes will also be assessed after 10 days in the surgical arm of the trial.
  - c. Surgical complications at 10 days, 6 weeks and 18 months after surgery: a list of possible complications is composed to score in a uniform way in all centers.
4. **Health-economic assessment:**
  - a. Work productivity and Activity Impairment Questionnaire at 6 weeks and 6 months after randomization.
  - b. Return to work at 6 weeks after randomization.
5. **Electrodiagnostics (EDX)** at 3 months and 9 months after randomization.
6. **Patient-reported outcome measures:** health-related quality of life (EQ5D-5L) at 6 weeks, 3 months, 6 months, 9 months and 18 months after randomization. Patient-reported outcome measurements will also be assessed after 10 days in the surgical arm of the trial.

For all secondary endpoints, baseline measurements will be obtained if applicable.

## 5 TRIAL DESIGN

### 5.1 Full-scale study design

The overall objective of the foot drop trial is to test the superiority of surgical release of the peroneal nerve at 10 +/- 4 weeks after symptom onset to maximal conservative treatment. The FOOTDROP trial is designed as a prospective, multicenter, randomized, parallel-design study. A double-blind design is not possible, given the fact that both the treating physician and the patient will always know the allocated treatment strategy. The clinical researcher (= outcome assessor) will be blinded for treatment.

Subjects will be randomized 1:1 to surgery or conservative treatment (simple randomization based solely on a single, constant 1:1 allocation ratio). If a patient, that signed the informed consent form (ICF), cannot be randomised because the foot drop has recovered, this will be documented in the eCRF. After randomization, the patients allocated to conservative treatment will enter a treatment period of approximately 9 months (individualised physiotherapy program). Patients allocated to the surgical arm will undergo surgery as soon as feasible after randomization (maximum within 1 week, preferably within 2 days). For all participating patients that signed the informed consent at the screening visit, an operation day will be scheduled, maximum one week after the randomization visit (due to practical scheduling reasons). At the moment of scheduling, the patient will be unaware of this date to prevent bias (and orientation of the mindset of patients toward surgery). If a patient is allocated to the conservative arm of the trial, the scheduled operation date will be cancelled, without knowledge of the patient. To facilitate signing of the informed consent form at the screening visit, patients will be informed prior to the consultation about the study (by telephone, through the patient brochure).

Patients in the surgical arm of the trial, are allowed to follow physiotherapy after surgery. The frequency and intensity are to be determined by the treating physician. All participants are allowed to use an ankle-foot orthosis. The use of electrostimulation is not advised, although not forbidden.

The endpoints will be evaluated at fixed time-points: 6 weeks, 3 months, 6 months and 9 months after randomization. Extended follow-up is scheduled 9 months after the primary endpoint is reached i.e. 18 months after randomization. Most trial assessments will be performed by the site-specific blinded researcher, ideally an independent physiotherapist. Patients allocated to the surgical arm of the trial will be evaluated 10 days after neurolysis. A postoperative control is considered standard of care. Sensorimotor function, quality of life and complications will be assessed during this postoperative control. Assessment of MRC-scores for ankle dorsiflexion and ankle eversion is considered standard of care and shall be performed by the treating physician. The treating physician can also assess ankle dorsiflexion strength measured by isometric dynamometry. This cannot be done by the outcome assessor because this would lead to unblinding.

A list of standard assessments (clinical records, considered daily practice = SOC; including motor and sensory function, ability to walk (barefoot), need for orthosis, treatment) will be composed for uniformity across centers. Standard assessments will be conducted at each study visit.

Cross-over is not allowed until the primary endpoint at 9 months is assessed. After the primary endpoint is assessed, cross-over from the conservative arm to surgery is allowed and patients will be treated according to standard of care (decision between treating physician and patient). Extended follow-up for all patients will be organised, 18 months after randomization. All primary and secondary endpoints, with the exception of electrodiagnostics, WPAI and return to work, will be assessed at 18 months. The End-of-Study (EOS) visit will take place at 18 months post-randomization. Cross-over patients will be followed-up as per protocol. All participating physicians and trial sites have the responsibility to guide patients throughout the study visits and are expected to follow protocol and to inform patients in a correct, objective manner. If the TSC documents an unusual high percentage of cross-over in a specific trial site, this trial site can be excluded from the foot drop trial.

Ninety-one patients will be enrolled in each arm of the trial, so that in total 182 patients will be enrolled in the foot drop trial. A blinded sample size reassessment by the trial statistician is planned when 50% of the planned patients have reached their 9 month visit or one month before the final patient would be

randomized, whichever occurs first. A dropout rate of 5% is anticipated, based on a large randomised trial with similar design (61, 62).

The foot drop trial is a multicenter trial. The number of participating centers will vary in function of the recruitment rate. In a first phase, 14 additional centers will be initiated apart from the pilot study centers. If recruitment is slower than expected, an additional 6 centers can be initiated. In other words; the study will run in 20 to 26 centers in Belgium and the Netherlands. The number of Dutch centers will be limited to 4 (phase 1 + phase 2).

### **Subgroup analysis**

A literature search was performed to identify predictors of good and bad outcome after surgical or conservative treatment. There is only limited data available and the data discussed come from several retrospective patient series (3, 38, 39, 43, 44, 63), one prospective conservative multicenter trial (28), one prospective case series (40) and one meta-analysis (58). Based on the cited articles, the following predictors of outcome will be used for further analysis:

1. Diabetes
2. Smoking (No, history, current)
3. Rapid/significant weight loss (> 5% of total body weight (18, 64))
4. High age (> 60 years)
5. Prolonged squatting

These predictors will be used in an exploratory analysis for the primary and key secondary endpoint (see Section 11). In this way, interactions between the predictor and a possible treatment effect can be identified and several new hypotheses can be generated to be investigated in further trials (where several subgroups could be studied in further detail).

-

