One multicenter prospective study of 46 patients (28) documented follow-up data in conservatively treated patients including 13 patients who did not receive any treatment at all due to mild symptoms. After a mean follow-up of 6 months, 39% of the conservatively treated patients (n = 33) needed a foot orthosis to be able to walk and 53% had a normal gait pattern. In patients in whom no conservative treatment was initiated 25% needed a foot orthosis and 63% had a normal gait pattern. Overall, 79% of patients with peroneal nerve entrapment reported improvement of ankle dorsiflexion at 6 months (n = 34). Taking all available literature into consideration, good outcome after conservative treatment for peroneal nerve entrapment varies between 53% and 100% in the literature. When interpreting these range of outcome percentages, one should realize that outcome measures differ between the studies. If data was available, good outcome was translated to an MRC-score  $\geq 4$  for ankle dorsiflexion. If data was not available, outcome measure of the study was documented.

Sangwan et al. (40) reported the results of conservative treatment of foot drop due to prolonged squatting in a prospective case series of 30 patients (34 limbs). Thirty-two foot drops fully recovered after 3 to 9 weeks. The other 2 patients recovered fully after 16 and 20 weeks (100%). Cruz-Martinez (9) prospectively documented the clinical evolution of foot drop in 30 patients receiving no or conservative treatment. Twenty-six patients fully recovered after a period of 3 weeks to 3 months, three other patients reported minimal weakness (97%). The severe muscle weakness in 1 patient did not improve after 6 months (but recovered within 2 weeks after neurolysis). Although these findings are not confirmed in other case studies, these series describe possible recovery of foot drop in an early stage with conservative therapy. These findings are important regarding the timing of randomization (see 5.1 full-scale study design).

Fares et al. (41) reviewed foot drop after bariatric surgery in 21 cases. Seven patients were treated conservatively and improved (100%). Two other foot drops resolved spontaneously. Since the degree of recovery was often not specified, this study was not included in Table 1.

Author	Type of study	Number of patients	Outcome measure	Good outcome (%)	Follow-up
Aprile (24)	Retrospective	14	Improvement ankle dorsiflexion or absence of gait difficulties	71%	3 months – 3 years

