## 8.6 Baseline data

Baseline data can be collected by the treating physician during the **screening visit** and will be recorded in the eCRF.

- EDX characteristics (see also 8.7.2.)
- Sex (male/female)
- Height in centimetres
- Age in years
- Site of entrapment (left/right/bilateral)
- Time since onset of foot drop in weeks
- MRC score for ankle dorsiflexion and ankle eversion at presentation
- Subacute onset (>2days) of foot drop
- Weight loss during last 6 months:

- Weight loss in kg
  - Current weight
  - BMI (kg/m^2)
  - Is weight loss intentional?
  - Weight loss after bariatric surgery?
  - Rapid onset?
- Postural neuropathy
  - Habitual leg crossing?
  - Prolonged squatting?
  - Frequent kneeling?
- Exercise (dynamic compression)
- Onset after childbirth?
- Previous lumbar surgery?
- Trauma
  - Sharp/blunt
  - Inversion trauma of the ankle
  - Knee dislocation
  - Other
- Iatrogenic causes of peroneal neuropathy
  - Surgery of the hip/knee/ankle
  - Other surgery (e.g. wrong positioning during thoracic surgery)
  - Recent bracing/ pneumatic compression device/ compression wrapping
  - Other
- Metabolic/systemic disease
  - Diabetes mellitus
  - Thyroid disease
  - Vitamin deficiencies e.g. B12
  - Oncological history
  - Other
- Prolonged bedrest
- Professional occupation
- Use of alcohol in units/week
- Tinel sign at the level of the fibular head
- History of neuromuscular diseases
- Professional disability
  - Currently employed/working?
  - Ability to continue working? (last day of work if the patient is unable to work)

**Baseline assessment** for the primary and secondary endpoints analyses will be collected at the **randomisation visit** by the **outcome assessor** (blinded researcher), this will reduce inter-observer variability during follow-up. The limited baseline assessments conducted by the treating physician should be conducted before the actual randomization to avoid bias. The EQ5D-5L is only to be registered if the patient did not complete the online survey or if the patient chose to not use the online system.

Baseline primary and secondary endpoint data will include:

- MRC-score for ankle dorsiflexion, hallux extension and ankle eversion
- Gait assessment:
  - o **Distance covered during the six-minute walk test (primary outcome)**
  - o Gait speed during the 10 meter walk test
  - o Ability to walk barefoot
  - o Stanmore questionnaire
  - o Need for foot-ankle-orthosis
  - o Functional ambulation categories

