### **8.7.2 Electrodiagnostics (EDX)**

Electrodiagnostic testing will be performed at baseline (screening visit, standard of care). After randomization, EDX will be repeated after 3 months and 9 months. EDX will be conducted by a trained neurologist/rehabilitation physician (see Section 6. Study Setting). EDX after randomization is not considered standard of care. The diagnosis of peroneal nerve entrapment is based on the screening EMG and falls outside the scope of the trial. However, electrophysiologists in the participating centers are advised to follow the 'guidelines' below.

In 2005, the American Association of Neuromuscular & Electrodiagnostic Medicine (AANEM) published a practice parameter for the use of EMG (electromyography) and NCS (nerve conduction studies) in evaluating patients with peroneal neuropathy (72), based on a thorough review of the literature. These recommendations however were based on Class III and IV evidence and classified as level C recommendations, reflecting the paucity of the literature on this topic (72, 73). Nevertheless, EDX was considered useful in making and/or confirming the diagnosis of peroneal neuropathy and in providing prognostic information. Following recommendations for electrodiagnostic techniques for diagnosing peroneal neuropathy were formulated:

- Peroneal motor NCS with assessment of conduction velocity through the fibular head and in the leg with recording from the anterior tibial (TA) muscle and extensor digitorum brevis muscle (EDB).
- Orthodromic and antidromic superficial peroneal sensory NCS
- At least one additional motor or sensory NCS in the same limb with normal findings (expert opinion)

The role of needle EMG in making a diagnosis remained questionable. However, experts suggest that abnormalities on needle examination outside of the distribution of the peroneal nerve should suggest alternative or additional diagnoses (6, 72).

No limits for abnormality were suggested in the literature, so following criteria were designed based on experience and previous trials in the literature (6, 10, 21, 74-76):

- Difference in motor nerve conduction velocity across the fibular head of more than 10 m/s  
AND/OR
- Presence of a motor conduction block: delta CMAP (compound motor action potential) amplitude across fibular head > 30%

Furthermore, the presence of and extent of axonal damage and mixed involvement needs to be studied, since these patients are expected to improve later and slower (1, 23).

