Following data will be collected in the eCRF (a paper source document is available to the local electrophysiologist):

- Difference in conduction velocity across the fibular head (m/s)
- Motor nerve conduction velocity (proximal and distal to the fibular head)
- CMAP distal motor latency
- Superficial peroneal sensory potential
- Conduction block: drop in amplitude (%)
- EDB-CMAP (in mV) (proximal and distal to the fibular head)
- Rest EMG abnormalities
- EMG during voluntary contraction abnormalities
- Evaluation of axonal damage
- Evaluation of mixed damage

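### The named exploratory predictors and the listed primary-model terms leave out baseline axonal or mixed nerve damage, which the protocol itself expects to slow recovery and records at screening

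*Protocol*

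**What the plan says.** Under "Subgroup analysis" in Protocol section 5.1, a literature search leads to a closed-looking list: "Based on the cited articles, the following predictors of outcome will be used for further analysis". The five entries are diabetes, smoking, weight loss above 5% of body weight, age above 60 and prolonged squatting. Their use is modest: "These predictors will be used in an exploratory analysis for the primary and key secondary endpoint", so that "several new hypotheses can be generated to be investigated in further trials".

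Section 8.7.2 says of the electrodiagnostic findings that "the presence of and extent of axonal damage and mixed involvement needs to be studied, since these patients are expected to improve later and slower". The eCRF items in the same section include "Evaluation of axonal damage" and a matching item for mixed damage. EDX is done at screening (sections 8.7.2 and 8.8), and section 8.6 counts its results as baseline data.

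Section 11.4.3 describes the primary analysis as a constrained longitudinal data analysis (cLDA) with terms for baseline, follow-up visit, treatment, and visit by treatment. No other baseline covariate is named. Section 8.3 specifies simple, unstratified 1:1 randomisation.

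On time since onset, section 8.6 records "Time since onset of foot drop in weeks" at screening. Section 1 reports early recovery in two conservative series and adds: "These findings are important regarding the timing of randomization".

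**The concern.** The protocol singles out one electrodiagnostic feature as prognostic and worth study, collects it before randomisation, and then uses its baseline value in no analysis that it lists. Three things follow.

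- **Precision.** A baseline variable that predicts the 9-month walking distance beyond baseline 6MWD removes residual variance when it is in the model. Left out, that variance stays in the treatment estimate.
- **Chance imbalance.** Simple unstratified randomisation of 182 patients does not guarantee balance on any single factor. A covariate named in advance protects against this more credibly than one added after the data are seen.
- **Effect modification.** The list exists to generate hypotheses on who benefits. If axonal damage is examined only after unblinding, the result carries less weight than one for the five named predictors.

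This is more than detail awaiting a SAP, because the protocol has itself chosen the predictors and set out the model terms.

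**Working it through.** **The plan's own figure.** Section 11.1 assumes an effect size of 0.5, two-sided 5%, 90% power and a t-test. The exact solution is 85.03 per arm, rounded up to 86, so 172 in total (power 0.903). For 5% dropout, 172 / 0.95 = 181.05, rounded up to 182. Both stated figures reproduce, and the change proposed here alters neither.

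**Power of an interaction with axonal damage.** The protocol gives no prevalence p, so 20% to 50% is assumed. In SD units of the 9-month change, with N = 172:

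SE = sqrt(4/(N·p) + 4/(N·(1 − p))); power for an interaction of 0.5 SD = Φ(0.5/SE − 1.96); smallest interaction detectable with 80% power = (1.96 + 0.84) × SE.

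| p | SE | Power at 0.5 SD | Detectable at 80% power |
|---|---|---|---|
| 50% | 0.305 | 37% | 0.85 SD |
| 30% | 0.333 | 32% | 0.93 SD |
| 20% | 0.381 | 26% | 1.07 SD |

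An interaction as large as the whole assumed main effect would therefore usually be missed. The same formula applies to the binary predictors already listed.

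**Onset time as a continuous predictor.** Sections 5.1 and 7.1 set entry at 10 ± 4 weeks, so weeks 6 to 14. Assuming a uniform spread, SD = 8/√12 = 2.31 weeks and the SE per week = 2/(√172 × 2.31) = 0.066. The slope detectable with 80% power is 0.185 SD per week, or 8 × 0.185 = 1.48 SD across the window.

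**Chance imbalance.** With 91 per arm, the SE of the difference in prevalence is sqrt(2·p·(1 − p)/91): 0.068 at p = 30% and 0.074 at p = 50%. An imbalance above 10 percentage points then has a probability of about 14% and 18%.

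**Precision.** If the variable explains a share R² of the variance left after baseline 6MWD, the confidence interval shrinks by the factor √(1 − R²). No document figure informs R². Purely as illustration, R² = 0 gives no gain, 0.10 gives 0.949 (about 5% narrower) and 0.20 gives 0.894 (about 11% narrower).

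**Cost in false positives.** For one endpoint, with independent unadjusted tests at 5%, the chance of at least one false positive is 1 − 0.95^5 = 23% for five predictors, 1 − 0.95^6 = 26% for six and 1 − 0.95^7 = 30% for seven.

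**The case against.** **The sections do not contradict each other.** Section 8.7.2 asks for axonal damage to be studied but does not promise a treatment-interaction test. EDX at 3 and 9 months is a secondary endpoint (section 4.3.2), and comparing electrophysiology is a stated objective (section 4.2). This stands. It does not explain why the baseline value, the one usable as a predictor, appears in no listed analysis.

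**The SAP may supply the terms.** Section 11.4.3 defers full details to a SAP that is not shown, and nothing in section 5.1 forbids further predictors. This also stands, so the point is an improvement to stated choices and not a claim that the analysis will never be done.

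**The reading is not standardised.** Centres are only advised to follow the EDX guidance, and the protocol gives no coding for axonal damage. This is a fair caution: a coding rule has to come first.

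**Time since onset.** A reader might infer that the protocol calls time since onset a driver of recovery within the entry window. It does not. In the squatting series "Thirty-two foot drops fully recovered after 3 to 9 weeks", with the last two patients recovering at 16 and 20 weeks. In the second series 26 of 30 recovered between 3 weeks and 3 months. The protocol uses these results to time randomisation. The only duration contrast in section 2 is poorer surgical outcome beyond 12 months, with no difference around 6 months. Both early-recovery series also relate to predictors already listed: squatting, and weight loss, which is in the title of the second.

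**Separating spontaneous recovery from need for surgery.** A reader might also infer that without these terms the trial cannot tell patients about to recover anyway from those who may need surgery. That goes too far. The data will exist either way, entry requires a persisting deficit, and later spontaneous recovery falls in both arms by randomisation. At 26% to 37% power, listing the terms would not achieve that separation either.

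**Conclusion.** The omission is real and firmly supported for axonal or mixed damage: the protocol states its prognostic role, asks for it to be studied and records it before randomisation, but leaves it off both the predictor list and the stated model terms. For onset time the support is indirect, so it is a secondary suggestion only.

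The treatment comparison is valid without these terms. The benefit is a gain in precision of unknown size, protection against chance imbalance, and a prespecified hypothesis-generating estimate. The power figures assume 172 evaluable patients, a prevalence of 20% to 50% and a common residual SD. The onset figure also assumes a uniform spread over weeks 6 to 14.

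**What to change.** 1. In section 8.7.2, define a simple coding of axonal or mixed damage on the screening EDX (for example present or absent, with criteria) and say how missing or indeterminate readings are handled.
2. In section 5.1, add this variable to the predictor list. Report the interaction estimates with confidence intervals for the primary and key secondary endpoints, and do not rely on p-values.
3. In section 11.4.3, add it as a prespecified baseline covariate with visit-specific effects in the primary cLDA.
4. Optionally, treat weeks from onset to randomisation in the same way, as a continuous variable. Section 8.6 records onset time at screening, so the interval from screening to randomisation must be added.

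The cost is protocol and SAP wording, the coding rule, a few model terms and one or two more exploratory tests, with the rise in false-positive risk shown above. No new assessment is needed.
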